introduce the study and ask if they are interested in learning more. If the patient agrees and would like more information about the study, the nephrologist/nurse practitioner will ask them to sign a DaVita “HIPAA Authorization to Use and Disclose Information for Research Purposes” form so their information may be shared with our study team and we can provide them with more information about the study. DaVita will provide the Program Manager with a list of eligible potential participants with signed DaVita HIPAA authorization forms. Our research team will contact patients on the list either by phone or in-person to discuss the study and if they are interested and agree to participate, they will provide informed consent and enrolled.

Participants will be enrolled at 4 locations in New York City: The Lower Manhattan Dialysis Center 1, The Lower Manhattan Dialysis Center 2, River Renal Services, Inc. and Chinatown Dialysis Center, LLC. The NYU Langone Health study team will analyze and collect data for this study.

Timeline: We will administer the interventions in two waves. In wave 2 (2 years after the start of the study), we will return to the dialysis centers in the first wave and begin enrollment again. This will allow us to identify new HD patients at each center. We will allow 1 month for identification of participants, initial contact by a research assistant, and baseline assessment as described below. Participants will be followed for 1 year after the end of the intervention for mortality and hospitalization.

Randomization:

We will randomize participants after completion of the baseline assessments. Participants will be block randomized (i.e., stratified over time) and stratified by sex, race/ethnicity, and dialysis center. They will be randomly assigned to one of the four study arms using a blind and secure computer based allocation system: **a) 6 months of CT alone, b) 6 months of ET alone, c) 6 months of CT+ET, d) standard of care.** We will use block sizes of four to ensure desired sizes in each arm. Given the nature of our interventions, it is not possible to blind the participant, treating provider and other HD center staff.

Intradialytic Interventions to Preserve Executive Function:

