The DSMB will be identified and managed through the ICTR and will be established and operated using the Guidance put forth by the US Food and Drug Administration "Guidance for Clinical Trial Sponsors: Establishment and Operation of Clinical Trial Data Monitoring Committees" (<https://www.fda.gov/downloads/RegulatoryInformation/Guidances/ucm127073.pdf>). The DSMB will be local and managed by the ICTR to allow for quick convening of meetings in the event of an unexpected result that raises concerns.

None of these individuals will be involved in the design or conduct of the trial. Any unanticipated problem or adverse event will be reported as outlined in JHU IRB policy 103.6(b). When possible the DSMB will be blinded to the study arm.

If any SAEs are more common in one of the three intervention arms compared to the standard of care arm, then the DSMB will consider termination of the study if the risks outweigh the benefits for participants. All SAEs that are deemed to have a causal relationship with the interventions in one of the arms of the study will be reviewed by the DSMB for the consideration of patient safety.

Planned DSMB Reviews:

The Data and Safety Monitoring Board (DSMB) shall review safety data during planned DSMB Data Review Meetings when 10%, 25%, and 50% of enrolled participants have completed 3 months of interventions and to analyze and review the interim analyses of these adverse events during active data collection. Data for the planned safety reviews will include, at a minimum, a listing of all reported AEs and SAEs. The DSMB will be informed of an Expedited Safety Report in a timely manner. The DSMB will have a final meeting at the end of the study.

We have performed a comprehensive literature search of published and unpublished manuscripts to identify possible side effects, adverse events, and serious adverse events of CT and ET interventions. No adverse events were noted in the literature search for side effects, adverse events or serious adverse events for CT. We theorize that the two most common risks associated with CT are the following: 1) boredom 2) frustration and 3) headache.

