There are greater risks associated with the ET intervention than with the CT intervention. The main risks associated with ET include: 1) Hypotension or low blood pressure which can cause dizziness and fainting. Hypotension can frequently occur during hemodialysis due to fluid removal. Hypotension is the most common risk of intradialytic ET and can occur in up to 33% of dialysis sessions in which exercise is involved, 2) cramping, muscle soreness, pain and fatigue, and 3) dyspnea or shortness of breath which occurs commonly during exercise. While hypertension and elevated heart rate were not noted as a risk associated with ET, we will also consider hypertension as a possible risk. Blood pressure reading of SBP>150 or DBP>90 mmHg will be considered as hypertension. SBP<110 or DBP<50 mmHg will be considered as hypotension. Heart rate that is consistently >80% of maximum heart rate will be considered as elevated.

Ad Hoc DSMB Reviews

In addition to the pre-scheduled data reviews and planned safety monitoring, the DSMB may be called upon for ad hoc reviews. The DSMB will review any event that potentially impacts safety at the request of the PI or NIDDK representative. In addition, the following events will trigger an ad hoc comprehensive DSMB Safety Review:

- Any death in the study which is considered possibly or definitely related to a study procedure.
- If any of the following adverse events occur at a significant higher rate than expected in the CT, ET, or CT+ET arm: muscle cramping, hypotension, or headache. We have outlined thresholds for pausing rules for rates of cramping, hypotension, hypertension, elevated heart rate, or headache which will trigger a mandatory pause in study enrollment for an unscheduled Data Safety and Monitoring Board review.

Cramping/Muscle Soreness: At the first day of each month, we will perform a Bayesian analysis of the ratio of cramping rates between ET arm (or CT+ET arm) versus the SC group. We will use a prior distribution of beta for each subgroup. We will then analyze the ratio of the distributions using a Monte

Carlo simulation. If there is 75% chance that [rate of cramping in the ET arm or CT+ET arm] divided by [rate of cramping in the SC arm] exceeds 1.10 (10% more in ET arm or CT+ET arm), we will pause the study pending DSMB recommendation.

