Hypotension: we will perform a Bayesian analysis of the ratio of hypotension rates between ET arm (or CT+ET arm) versus the SC arm. We will use a prior distribution of beta(0,0) for each subgroup. We will then analyze the ratio of the distributions using a Monte Carlo simulation. If there is an 75% chance that [rate of hypotension in the ET arm or CT+ET arm] divided by [rate of hypotension in the SC arm] exceeds 1.15 (15% more in ET arm or CT+ET arm), we will pause the study pending DSMB recommendation.

Hypertension: At the first day of each month, we will perform a Bayesian analysis of the ratio of hypertension rates between ET arm (or CT+ET arm) versus the SC arm. When calculating hypertension rates, we will exclude dialysis sessions with starting blood pressure being hypertensive. We will use a prior distribution of beta(0,0) for each subgroup. We will then analyze the ratio of the distributions using a Monte Carlo simulation. If there is an 75% chance that [rate of hypertension in the ET arm or CT+ET arm] divided by [rate of hypertension in the SC arm] exceeds 1.15 (15% more in ET arm or CT+ET arm), we will pause the study pending DSMB recommendation.

Elevated Heart Rate (EHR): At the first day of each month, we will perform a Bayesian analysis of the ratio of EHR rates between ET arm (or CT+ET arm) versus the SC arm. We will use a prior distribution of beta (0,0) for each subgroup. We will then analyze the ratio of the distributions using a Monte Carlo simulation. If there is an 75% chance that [rate of EHR in the ET arm or CT+ET arm] divided by [rate of EHR in the SC arm] exceeds 1.08 (8% more in ET arm or CT+ET arm), we will pause the study pending DSMB recommendation.

Headache: At the first day of each month, we will perform a Bayesian analysis of the ratio of headache rates between CT arm (or CT+ET arm) versus the SC arm. We will use a prior distribution of beta(0,0) for each subgroup. We will then analyze the ratio of the distributions using a Monte Carlo simulation. If there is an 75% chance that [rate of headache in the CT arm or CT+ET arm] divided by [rate of headache in the SC arm] exceeds 1.12 (12% more in CT arm or CT+ET arm), we will pause the study pending DSMB recommendation.

After review of the data, the DSMB will make recommendations regarding study conduct and/or continuation.

Temporary Suspension of enrollment for Ad Hoc DSMB Safety Review

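### Safety pausing rules: the beta(0,0) prior leaves an arm with zero events undefined, and with no stated operating characteristics a chance pause is likely under most assumptions

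*Combined protocol and SAP*

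**What the plan says.** The rules are in the protocol under Ad Hoc DSMB Reviews. Each compares the session-level event rate in an active arm with standard of care (SC) and acts when the posterior chance of exceeding a ratio margin reaches 75%. The cramping rule, for example, begins: "If there is 75% chance that [rate of cramping in the ET arm or CT+ET arm] divided by". The margins are 1.10 (cramping), 1.15 (hypotension and hypertension), 1.08 (elevated heart rate) and 1.12 (headache). Cramping, hypotension, hypertension and heart rate involve the ET or CT+ET arm; headache involves the CT or CT+ET arm.

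- **Prior.** Four rules: "We will use a prior distribution of beta(0,0) for each subgroup". Cramping: beta, no parameters.
- **Looks.** Four rules are monthly, for example "At the first day of each month, we will perform a Bayesian analysis of the ratio of headache rates between CT arm". The hypotension rule starts without a schedule: "Hypotension: we will perform a Bayesian analysis of the ratio of hypotension rates between ET arm".
- **Unit.** It is only implied, by the hypertension rule: "we will exclude dialysis sessions with starting blood pressure being hypertensive".
- **Consequence.** The individual rules speak of pausing the study. The paragraph that introduces them, and the later section on temporary suspension, speak of enrolment only.
- **Entry.** Timeline: "We will administer the interventions in two waves", and "We will allow 1 month for identification of participants, initial contact by a research assistant, and baseline assessment as described below". The second wave comes two years after the start.

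The section does not cover zero events in an arm, minimum exposure, repeated looks, repeated sessions of one participant, or an expected false-pause rate.

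**The concern.** There are two separate problems. First, beta(0,0) is improper and stays improper until an arm has at least one event and one non-event. Early looks at infrequent events are where that fails, and the plan gives no fallback, so the result depends on the software or on an unrecorded decision.

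Second, a 75% cut-off with margins close to 1 is easy to cross by chance when few sessions have accrued. Several rules are looked at month after month, and sessions within a participant are treated as if independent. If most trials with no excess would trigger at least once, a trigger says little about whether an event is truly more frequent. Each trigger also brings a mandatory enrolment halt at all centres until the DSMB has met.

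**Working it through.** The plan states no operating characteristic, so there is no figure to reproduce.

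**Inputs from the protocol:** priors, margins, 75% cut-off and monthly looks as above; about 200 participants, so 50 per arm; HD 2-3 times weekly; six months of intervention. The only base rate is in Planned DSMB Reviews: hypotension in up to 33% of exercise sessions.

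**Assumptions:** 13 sessions per month; cumulative data; the session as unit; hypotension also looked at monthly; beta(0,0) also for cramping. Session rates in the order cramping / hypotension / hypertension / elevated heart rate / headache are low 5/20/25/2/5%, high 10/33/35/5/10%, or all 33%. Within-participant correlation (ICC) is 0 or 0.05. An undefined look counts as no pause.

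**1. Zero events.** With 0 events in n sessions the posterior is Beta(0+0, 0+n) = Beta(0,n). numpy refuses the draw (a <= 0) and scipy returns nan for the mean. The chance of no SC events, with independent sessions, is (1-p)^n. At p = 3% this is 0.97^40 = 30% after 40 sessions and 0.97^100 = 5% after 100. At p = 1% it is 67% and 37%.

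**2. One comparison, small counts.** Take 4 versus 2 headaches in 39 sessions per arm (three participants for one month, 3 x 13). The posteriors are Beta(4,35) and Beta(2,37), and P(ratio > 1.12) = 78%, a pause. Under beta(0.5,0.5) they are Beta(4.5,35.5) and Beta(2.5,37.5), giving 76%, still a pause.

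**3. One look, no true excess.** On the log ratio, se = sqrt(2(1-p)/(np)), and the chance of firing is 1 - Phi(log(margin)/se + 0.674). For headache at p = 3% and n = 200 sessions per arm, se = sqrt(1.94/6) = 0.569; log(1.12)/se = 0.199; 1 - Phi(0.874) = 19.1%. With cramping 5%, hypotension and hypertension 20%, and heart rate and headache 3%, the five chances are 18.6, 8.5, 8.5, 20.9 and 19.1%. The chance that none of the five fires is 0.814 x 0.915 x 0.915 x 0.791 x 0.809 = 0.436. So at least one of five fires with probability 56%, and at least one of ten with 1 - 0.436^2 = 81%. At the full 3,900 sessions per arm (50 x 78) these become 20% and 36%. Independence between comparisons is an approximation, because they share the SC arm.

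**4. Repeated looks, no true excess** (simulation of the rules, active arms tested separately; ranges span low and high rates; last column is a zero-event look in a beta(0,0) rule at any time):

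| Entry | Pause, ICC 0 | Pause, ICC 0.05 | Pause, all 33%, ICC 0 | Pause, all 33%, ICC 0.05 | Zero-event look |
|---|---|---|---|---|---|
| Two one-month waves | 84-92% | 94-97% | 45% | 82% | 0-3% |
| Waves over 3 months | 92-97% | 99-100% | 71% | 93% | 1-43% |
| Waves over 6 months | 96-99% | 99-100% | 89% | 98% | 20-87% |
| 5 per month | 99-100% | 99-100% | 99% | not given | 90-100% |

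With all rates at 33%, zero-event looks occur in 0% of trials in the first three rows and 4% in the last (ICC 0).

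**5. Sensitivity.**
- *Pooled arms, five comparisons.* Low/high rates mostly give 78-100%; the lowest one-month-wave runs give 72-73%.
- *Spread of entry within the month.* With all rates 33%, ICC 0 and one-month waves, runs give 45, 65, 68 and 72% tested separately and 33, 39 and 40% pooled. The result depends on an entry pattern that the plan does not fix.
- *Hypotension left out*, as it has no schedule (one-month waves, low/high): 83-90% at ICC 0 and 93-97% at ICC 0.05.
- *Beta(0.5,0.5) in place of beta(0,0)* (one-month waves, low/high): 90/84% against 92/84% at ICC 0, and 98/95% against 97/94% at ICC 0.05. The prior does not drive the false pauses.

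**The case against.** A sensitive safety trigger can be a deliberate choice. The pause is temporary, the board includes a statistician, and it is local "to allow for quick convening of meetings in the event of an unexpected result that raises concerns". That stands: the gap is the missing operating characteristics, not the sensitivity itself.

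Four of the five base rates, the entry pattern, cumulative data and the unit are assumptions. Correlation between event types, which was not modelled, would tend to lower the chance of at least one pause. That also stands, and it is why the result is conditional.

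If each wave really enters within one month, there is almost no enrolment left to halt. In a run of that reading, no pause fell while enrolment was open; under slower entry most did. So the harm matters mainly with staggered entry. The one month could also mean one month per centre, and the SAP reports 121 randomised with enrolment from 09/2018 to 02/2023, which is slow entry.

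A reader might infer more than the documents support:
- *That the improper prior causes the false pauses.* Changing it leaves them unchanged.
- *That ten comparisons are planned.* The wording with *or* also allows pooled arms, hence five.
- *That a trigger stops the trial, or that these rules ended it.* The suspension section describes a temporary enrolment halt, and the SAP attributes termination to COVID-19 restrictions.

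**Conclusion.** The concern holds in a conditional form. As written, four rules cannot be evaluated when an arm has no events, and the cramping prior is unspecified. How often this occurs runs from almost never (rapid entry, common events) to nearly always at some early look (slow entry, low rates).

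At least one pause without any true excess is likely under most assumptions. It is roughly 80-100% at session rates of 2-35%, whether arms are tested separately or pooled, and about 40-70% in the favourable corner of all rates at 33%, independent sessions and one-month waves. An unconditional claim would go too far, since only the hypotension rate is documented. The consequence is avoidable temporary enrolment halts and unscheduled reviews.

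**What to change.** 1. State one proper prior, such as beta(0.5,0.5), in all five rules. This is nearly free and cures only the zero-event case.
2. State the unit of analysis, and account for repeated sessions with a participant-level variance or random effect.
3. Set one look schedule for all five rules and a minimum exposure before the first look. Say whether the active arms are tested separately or pooled.
4. Give the DSMB simulated false-pause and detection probabilities for all five events. Leave the cut-off, margins and acceptable false-alarm rate to the board.
5. Reconcile the rules that pause the study with the text that pauses or halts enrolment.

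Because the SAP reports that the trial has ended, the practical step now is to document how the rules were run, and to make these changes before they are reused.

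**Cost.** Some simulation work, and slower or missed triggering for small excesses. To illustrate the trade-off: with participant-level variance (normal approximation on the log ratio), a first look at 10 or more participants per arm with three months of sessions, one-month waves and ICC 0.05, false pauses for the whole rule set are 78-87%, 26-33% and 6-10% at cut-offs of 75, 95 and 99%. At a true ratio of 1.5 (ICC 0-0.05, both compared arms in excess), hypotension is detected by trial end in 98-100% at the 95% cut-off and 92-100% at 99%; cramping in 68-100% and 46-100%. Rarer events lose most. One look at full data (ratio 1.5, ICC 0.05) detects elevated heart rate at a 2% base rate in 41% and 18%, and headache at 5% in 59% and 30%; monthly looks would raise these somewhat.

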All participants provided written informed consent and were compensated with \$10 (funding from NIDDK R01DK114074). This trial was approved by the Johns Hopkins Institutional Review Board (IRB00152858) and sIRB with NYU, and reviewed by the Fresenius Medical Care Holdings, Inc. Investigator Initiated Trials Review Committee and DaVita Clinical Research. COVID-19 restrictions in dialysis facilities between 2020-2022 affected recruitment and study operations, leading to the Data and Safety Monitoring Board (DSMB) recommendation of trial termination. Therefore, this trial was terminated on 12/08/2023. The study was registered at [clinicaltrials.gov](https://clinicaltrials.gov/ct2/show/NCT03616535) (NCT03616535).

Eligibility

We recruited English-speaking adult (≥18 years) patients with ESKD who had initiated thrice weekly hemodialysis within 3 months to 3 years (09/2018-06/2022) at 14 dialysis centers in the Baltimore, Maryland area and 1 dialysis center in New York City, New York. We limited the study to participants with 3 months-3 years of hemodialysis to capture a population that had potentially reversible cognitive impairment. Exclusion criteria were: 1) inability to participate in ET without assistance; 2) conditions limiting participation (pregnancy, angina pectoris, chronic lung disease requiring oxygen, musculoskeletal conditions, lower- or upper-extremity amputation, orthopedic disorders exacerbated by physical activity, femoral vascular access, legally blind, inability to recognize numbers and letters as well as hepatitis B infection requiring medical isolation); and 3) incarceration.

Randomization

After the baseline assessment, 121 participants were block-randomized (based on sex, race, and dialysis center, factors chosen to remove their effects on cognition) into 4 arms using a secure computer-based allocation system (R).

Statistical Analysis

Baseline characteristics of participants were presented by arm and compared using ANOVA test for normally distributed continuous variables, Kruskal-Wallis test for nonnormally distributed continuous variables, and Chi-squared test for categorical variables. Differences in the primary and secondary outcomes were tested using these methods as well.

For CT, ET and CT+ET arms, we evaluated each participant's adherence to the assigned intervention as: the number of dialysis sessions that the participant attended and participated in the intervention/the number of dialysis sessions that the participant attended)*100%.

The effect of interventions was analyzed according to the intention-to-treat principle. Changes in executive function, global cognitive function, ESKD-specific clinical outcomes, and patient-centered outcomes between baseline and 3 months were handled as continuous outcomes. After visually verifying the linearity, normality, and equal variance assumption, we used linear regression to test the main effect of CT alone and the main effect of ET alone as well as the interaction between CT+ET compared with SC; we also tested these effects with an ANCOVA analysis. In addition, we tested whether the impact of CT, ET, and CT+ET differed from each other. The main comparison used models adjusted for age at enrollment, education, and baseline measures of outcomes, which were adapted to account for imbalances between groups with respect to important risk factors for the outcomes.

All analyses were performed using Stata 16.1 (StataCorp, College Station, TX). Statistical significance was defined as a two-sided p-value <0.05. There was no missingness in adjusted covariates.

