2.1. Time to Event Outcomes: Mortality. To examine the univariate association between study arm and mortality, separate product-limit estimated cumulative incidence curves will be calculated. Next, we will use a Cox proportional hazards model to estimate the association of study arm with time to the development of mortality. Censoring will occur at loss to follow-up or KT. The hazard function for the Cox model is:

$$\lambda(t|X_i) = \lambda_0(t) \exp(X_i \beta)$$

where x_i is the value of the covariate X for the i th participant, and $\lambda_0(t)$ is the baseline hazard function. If the proportional hazards assumption is not met, we will include an interaction with time.

2.2. Dichotomous Outcomes: Poor Lower Extremity Function, poor HRQOL, return to work, and amputation. We will test whether the study arm is associated with poor lower extremity function, poor HRQOL, return to work, and amputation using logistic regression or a modified Poisson regression (145), if the outcome is $>10\%$.

2.3. Count Outcomes: Number of Falls and Hospitalizations. We will use Poisson regression to test whether the study arm is associated with the number of falls and hospitalizations within the 3 months of the intervention.

3.0. Analytic Methods: Effect of CT, ET, and CT+ET on patient-centered outcomes.

Change in Patient-centered Outcome: For each patient-centered outcome, we will calculate a score. We will treat each patient-centered outcome as continuous and will estimate the change in these outcomes between baseline and 3 months. We will analyze each patient-centered outcome separately. We will analyze the change in these outcomes using the analytic plan described in 1.0.

3.1. Change in Patient-centered Outcome over 6 Months. Patient-centered outcomes are longitudinal data (3 and 6 months) and analyzed using the analytic plan described in 2.0 for repeated measures of executive function.

4.0. Treatment Effect Heterogeneity. Frailty has been associated with worse trajectories of executive function in older adults (146) and HD patients (16). Therefore, we will explore treatment heterogeneity between those who are frail and nonfrail in all primary and secondary outcomes. We will include an interaction term between frailty status and intervention type (study arm) to assess difference in treatment effect by frailty status. Using a similar approach, we will test for treatment effect heterogeneity by age, sex, and race/ethnicity.

Risks:

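### The SAP update's continuous-change rule for ESKD-specific clinical outcomes contradicts protocol sections 2.1–2.3, and the update does not say which text governs

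*Combined protocol and SAP*

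**What the plan says.** Protocol section 2.0 introduces the ESRD-specific clinical outcomes and divides them into three types.

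- **Section 2.1, mortality:** "we will use a Cox proportional hazards model to estimate the association of study arm with time to the development of mortality", with censoring at loss to follow-up or transplant.
- **Section 2.2, dichotomous outcomes:** "We will test whether the study arm is associated with poor lower extremity function, poor HRQOL, return to work, and amputation using logistic regression", or modified Poisson regression when the outcome exceeds 10%.
- **Section 2.3, counts:** falls and hospitalizations, by Poisson regression.

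Patient-centered outcomes are a separate family, in section 3.0.

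The SAP update (Statistical Analysis) names the same clinical family, now with the term ESKD, alongside the cognitive and patient-centered outcomes. It says that changes in "ESKD-specific clinical outcomes, and patient-centered outcomes between baseline and 3 months were handled as continuous outcomes". The model follows: "After visually verifying the linearity, normality, and equal variance assumption, we used linear regression", with an ANCOVA as well. On covariates it says: "The main comparison used models adjusted for age at enrollment, education, and baseline measures of outcomes".

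The update does not list the ESKD-specific outcomes, and it names no Cox, logistic or Poisson model. Its paragraph on comparing baseline characteristics includes a "Chi-squared test for categorical variables" and adds: "Differences in the primary and secondary outcomes were tested using these methods as well".

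**The concern.** The same family of secondary outcomes now has two incompatible specifications. Under the protocol none of its members is a continuous change score; under the update the family is analysed as one.

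Two things are at stake. First, for several members the continuous rule is the wrong type of model: normal errors for an uncommon yes/no event, a baseline covariate that may not vary, and no use of time at risk. Second, nothing states which text takes precedence, so the model for each of these outcomes can be chosen after the data are in. The reason given for the update, the COVID-19 shutdowns, does not explain a change of outcome type.

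**Working it through.** The plan gives no figure to reproduce. The check sets the two texts side by side, outcome by outcome.

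| Outcome | Protocol model | Does a baseline-adjusted continuous change fit? |
|---|---|---|
| Mortality | Cox (2.1) | No. Everyone is alive at baseline, so the baseline value is constant and the change is simply death, yes or no. Survival time is unused. |
| Amputation | Logistic or modified Poisson (2.2) | No. Amputation is an exclusion criterion in both the protocol and the update, so the baseline is constant and the change is a 0/1 event. |
| Return to work | Logistic or modified Poisson (2.2) | Poorly. Table 2 lists ability to return to work at baseline, 3 and 6 months, so a change and a baseline covariate exist, but the outcome is categorical. |
| Falls, hospitalizations | Poisson (2.3) | Poorly. These are counts over a period, not scores. |
| Poor lower extremity function, poor HRQOL | Logistic or modified Poisson (2.2) | Yes, if the underlying SPPB or KDQOL score is used, but that is a different endpoint from the dichotomous one in 2.2. |

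**What the chi-squared provision adds.** It gives an unadjusted arm comparison for amputation, return to work and death by 3 months. It does not give the effect estimates planned in sections 2.1 and 2.2, the factorial contrasts or any use of time at risk.

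It is also weak for uncommon events. Inputs: 121 randomised to 4 arms (SAP update, Randomization), and a 3-month event risk of 2–5%, which is an assumption because the documents give no such risk.

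- Participants per arm: 121 / 4 = 30.25.
- Expected events per arm at 2%: 30.25 × 0.02 ≈ 0.6.
- Expected events per arm at 5%: 30.25 × 0.05 ≈ 1.5.
- Risk needed for an expected 5 events per arm: 5 / 30.25 ≈ 0.165, about 17%.

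**Why time at risk matters.** The update reports 25 interrupted 3-month follow-ups. If all belong to the randomised group, that is 25 / 121 ≈ 21%. Section 2.1 censors at transplant. The protocol's Timeline follows participants for mortality and hospitalization for 1 year after a 6-month intervention, or about 6 + 12 = 18 months. The update's Study Design places primary and secondary outcomes at 3 months.

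**The case against.** The strongest reply is that the update never withdraws sections 2.1–2.3. It says the methods were updated for the shutdowns, and its sentence concerns changes, so it can be read as covering only outcomes with a change score. On that reading Cox, logistic and Poisson remain in force. The first part stands: replacement is an inference from silence. The second stands only in part. The protocol's clinical family contains no scored outcome: lower extremity function and HRQOL enter it only as dichotomies, and the patient-centered scores are a separate family that the update also names separately. The scored-only reading is therefore itself an unstated redefinition.

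Other replies also have force.

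- The chi-squared provision means that categorical outcomes would have some test even if the protocol models were gone.
- A constant covariate would normally be dropped by the software and would not bias the arm contrast. The fault lies in the model type, not in a fit that breaks down.
- The update mentions a visual check of assumptions before linear regression. It names no alternative if the check fails.
- With so few expected events at 3 months, any model would be nearly uninformative at that horizon.
- Missing change scores after death are a separate matter, partly covered by the competing-event sensitivity analyses under Statistical Methods and, for cognition, by section 1.1.

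A reader might infer that mortality, amputation and return to work have no valid analysis, or that the survival comparison has been deleted. The documents do not support either: sections 2.1–2.3 still stand in the combined document, and return to work has a baseline measure.

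**Conclusion.** The contradiction is real, and it concerns secondary outcomes only. One named family has two specifications with no order of precedence. The continuous rule is unsuitable for two outcomes (mortality and amputation) and a poor fit for three more (return to work, falls and hospitalizations). For lower extremity function and HRQOL it changes the endpoint from dichotomous to continuous without saying so.

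This conclusion rests on the text and does not depend on the assumed 2–5% risk, which only shows how little the chi-squared tests could offer at 3 months. Mortality would lose its time-to-event analysis only if the update were meant to replace the protocol's methods in full, and it does not say that. The change in the Trail Making Test, the primary outcome, is unaffected. The point should be corrected, but it does not threaten the trial's main conclusion.

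**What to change.** In the Statistical Analysis section of the SAP update:

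1. List each ESKD-specific clinical outcome with its model and time horizon.
2. Limit the continuous-change rule to scored outcomes: the cognitive tests, SPPB, KDQOL and PROMIS-29.
3. State that any continuous scoring of lower extremity function and HRQOL departs from, or is additional to, the dichotomous definitions in section 2.2.
4. State that section 2.1 still applies to mortality as a time-to-event outcome, section 2.2 to amputation and return to work, and section 2.3 to falls and hospitalizations. Use exact or penalised methods where events are few, and omit the baseline-outcome covariate where it is constant.
5. If any of these outcomes was dropped, name it and give the reason.

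The cost is a short wording change and running models that the protocol, for the most part, already specifies. The exact or penalised versions are the only additions. No new data are needed.
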